9.0 Procedures Involved

9.1 *Describe and explain the study design.*

24 hours before the scheduled appointment participants will be called to ask COVID screening questions. Parents will be spoken to unless the child has research age 18 and has signed consent to participate in the study as an adult. Should no one respond to our call, and automated email will be set to the email address on file and a redcap survey will administer the COVID screening survey. Staff will review responses and reschedule families if anyone in the household has had symptoms in the past 14 days. (see attached survey)

Upon arrival for a scheduled appointment, participants will ring the door bell and a staff member in PPE will meet them for touchless temperature screening and COVID screening questions. A Yes to any of the questions or recording a temperature >100 on Parent or child will lead to suggesting the family call their health care provider immediately and rescheduling of the appointment to a date 14days+ after symptoms have subsided for anyone in the household.

Only one family will be scheduled at a time. Appointments will be separated by 30 min to allow for deep cleaning and sanitation.

SNAK STUDY PART 1 (Visits 1-9)

Appointment 1 (2.5-3 hrs) (TODAY)

- *Consent and Assent Process*
- *Parent/guardian and child will answer some questions separately. Including, completing a pubertal assessment of child's current development, as well as a food security survey.*
- *Parents/guardians will then complete a Demographic Questionnaire and a Child Feeding Questionnaire and have their own height and weight measured.*
- *The child will:*
 1. *answer a stress questionnaire, a risk taking questionnaire, food consumption, and a healthy eating questionnaires*
 2. *have their body composition measured in the BODPOD*
 3. *have their heart rate and blood pressure measured*
 4. *be asked to exercise on a variety of gym equipment for a few minutes*
 5. *be asked to rate a variety of snack foods*
 6. *provide a recall previous 24-hour diet and physical activity*

Appointment 2 (30-45min)

The child will:

1. *be asked not to eat or drink anything other than water for 2 hours prior to the appointment*
2. *be asked to eat a granola bar and play a computer game for a small snack food reward or activity time*
3. *provide a recall of previous 24-hour diet and physical activity*
4. *sent home with 2-weeks' worth of snacks and asked to eat a snack each day*

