5. *be instructed to answer 7 short survey questions via email, text or online survey each evening*

Appointment 3 (30-45min)

The child will:

1. be asked not to eat or drink anything other than water for 2 hours prior to the appointment
2. *be asked to eat a granola bar and then play a computer game for a snack food reward (30g each) or activity time*
3. *provide a recall of same day diet and physical activity and fill out a short online survey*
4. *be sent home with a watch that tracks activity and asked to wear it for 1 week, without removing it, until their next appointment*
5. *be instructed to keep track of their food and beverage intake during the week using a provided booklet*

Appointment 4 (30-45min)

The child will:

1. be asked not to eat or drink anything other than water for 2 hours prior to the appointment
2. *be asked to eat a granola bar and play a computer game for a small snack food reward or activity time*
3. *provide a recall of previous 24-hour diet and physical activity*
4. *sent home with 2-weeks' worth of snacks and asked to eat each day*
5. *be instructed to answer 7 short survey questions via email, text or online survey each evening*

Appointment 5 (30-45min)

The child will:

1. *be asked not to eat or drink anything other than water for 2 hours prior to the appointment*
2. *be asked to eat a granola bar and then play a computer game for a snack food reward activity time*
3. *provide a recall of same day diet and physical activity and fill out a short online survey*
4. *Parent and child will be paid for your first wave of participation (Appointments 1-5).*

FOLLOW UP VISIT

Appointment 6 (90min, 6 months after initial appointment)

The Parent will:

1. *complete the pubertal assessment, eating questionnaires, child feeding questionnaires, a health change form, and have their height and weight measured.*

The child will:

1. *complete the pubertal assessment, stress questionnaire, and eating questionnaires*
2. *have their body composition measured*
3. *have their heart rate and blood pressure measured*
4. *provide a recall of previous 24-hour diet and physical activity*
5. *be paid for their follow up visit participation*

Appointment 7 (90min, 15 months after initial appointment)

The Parent will:

1. *complete the pubertal assessment, eating questionnaires, child feeding questionnaires, a health change form, and have their height and weight measured.*

The child will:

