To test our primary hypotheses related to zBMI change over time, appointments (level 1) were nested within individuals (level 2) and models included month of visit, sex, DEBQ score, pubertal development score and baseline zBMI as fixed effects. Our dependent measure was zBMI at baseline and 6, 15, and 24 months. We used number of months between visits as our marker of time (i.e. 6, 15, and 24). To test hypotheses related to sensitization, we categorized people as “sensitizers” (> 1) or “satiators” (≤ 1) depending on their change in RRV of food from baseline to post. This threshold was chosen to account for participants who increased responding from baseline to post, even by a small amount, while allowing participants who did not change responding or who decreased responding to be considered together as satiators. To test hypothesis 1, we included HED sensitization in the model and examined interactions with time. To test hypothesis 2, we included LED sensitization in the model and examined interactions with time. To test hypothesis 3, we included both HED and LED sensitization in the model, we interacted each one individually with time, and we interacted them with each other and with time. Finally, to test hypothesis 4, we added DD as a fixed effect and interacted it with HED sensitization and visit to examine moderation.

- 1) Temple, J. L. Factors that influence the reinforcing value of foods and beverages. *Physiol. Behav.* **136**, 97-103, doi:10.1016/j.physbeh.2014.04.037 (2014).
- 2) Clark, E. N., Dewey, A. M. & Temple, J. L. Effects of daily snack food intake on food reinforcement depend on body mass index and energy density. *Am. J. Clin. Nutr.* **91**, 300-308, doi:10.3945/ajcn.2009.28632 (2010).

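### The SAP codes time as scheduled months, mislabels it and renames it for hypothesis 4; actual months elapsed since Visit 1 should be used in all four models

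*SAP*

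**What the plan says.** All the relevant SAP text is in the analytic plan that follows the sample-size statement.

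- Outcome occasions: "Our dependent measure was zBMI at baseline and 6, 15, and 24 months".
- Time variable: "We used number of months between visits as our marker of time (i.e. 6, 15, and 24". Baseline has no value in this list.
- Fixed effects: "models included month of visit, sex, DEBQ score, pubertal development score and baseline zBMI as fixed effects".
- Hypothesis 1: "we included HED sensitization in the model and examined interactions with time". Hypotheses 2 and 3 also use the word *time*.
- Hypothesis 4: "to test hypothesis 4, we added DD as a fixed effect and interacted it with HED sensitization and visit to examine moderation".

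Protocol Section 9.1 sets the schedule. The first follow-up reads "Appointment 6 (90min, 6 months after initial appointment", and Appointments 7 and 8 are placed in the same way at 15 and 24 months. Section 22.5 confirms a 9-month gap between the first two follow-ups. The COVID screening rule in Section 9.1 provides for "rescheduling of the appointment to a date 14days+ after symptoms have subsided for anyone in the household". Neither document gives a visit window, says how an off-schedule visit is coded, or reports when visits took place.

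**The concern.** All four hypotheses are tested as interactions with time, so the definition of time is part of each estimand. As written it leaves three things open.

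1. The label and the values disagree. The values are cumulative from Visit 1, while the label describes intervals.
2. Baseline zBMI is both an outcome occasion and a covariate, yet only three time values are listed. The reader has to infer that baseline rows enter at 0.
3. The time term has more than one name, and hypothesis 4 does not say whether *visit* means months, a visit index or a categorical factor.

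Behind the wording lies a choice of method. The natural reading of three fixed values is that each visit was given its scheduled month. A visit held late is then treated as if it had been on time, and the extra growth is credited to too short a period. The postponements that the protocol describes can only make visits later. If lateness also differed between sensitizers and satiators, their slopes would be stretched by different amounts and part of the interaction would be an artefact.

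**Working it through.** **Reproducing the SAP's values.** The intervals in protocol Section 9.1 are 6, 9 and 9 months. Their running sums are 6, 6 + 9 = 15 and 15 + 9 = 24. The listed values therefore reproduce exactly as scheduled months since Visit 1, and do not reproduce as intervals.

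**Effect of late visits.** Inputs: scheduled codes 0, 6, 15, 24 (baseline taken as 0), and assumed delays, because the documents give none. Further assumptions: complete data, zBMI linear in actual elapsed months, other covariates ignored. The ratio of fitted to true slope is then

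ratio = Σ(code − mean code) × actual time ÷ Σ(code − mean code)².

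The mean code is (0 + 6 + 15 + 24)/4 = 11.25. The centred codes are −11.25, −5.25, 3.75 and 12.75. Their squares sum to 126.5625 + 27.5625 + 14.0625 + 162.5625 = 330.75.

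For delays d₁, d₂, d₃ at the three follow-ups:

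ratio = 1 + (−5.25d₁ + 3.75d₂ + 12.75d₃)/330.75.

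| Assumed delay (months) | Numerator | Ratio |
|---|---|---|
| 0.5 at every follow-up | 5.625 | 1.017 |
| 1 at every follow-up | 11.25 | 1.034 |
| 2 at every follow-up | 22.5 | 1.068 |
| 3 at every follow-up | 33.75 | 1.102 |
| 1, 2 and 3 in turn | 40.5 | 1.122 |
| 3 at the 24-month visit only | 38.25 | 1.116 |
| Mean zero, SD 1 or 2 | 0 expected | 1.000 |

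A uniform delay thus costs about 3.4% per month. The last row was also simulated and gave 0.9999 and 1.0001.

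**Why the baseline code matters.** If baseline rows are left out, the codes are 6, 15 and 24, centred at −9, 0 and 9. A uniform delay d then adds (−9 + 0 + 9)d = 0, and the ratio is 1.000. The effect of a uniform delay therefore depends on whether baseline enters at 0, which the SAP does not state.

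**The interaction.** If lateness is the same in both groups, both slopes are multiplied by the same ratio k, and their difference becomes k × (true difference). Zero stays zero, and a real difference per month is overstated by the same percentage. If one group is late by 1, 2 and 3 months and the other is on time, equal true slopes appear as 1.122 and 1.000, a false difference of 12% of the slope.

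**Hypothesis 4.** Suppose *visit* is an index 0, 1, 2, 3. Its centred values are −1.5, −0.5, 0.5 and 1.5, with squares summing to 5. The cross-product with scheduled months is −3 + 7.5 + 36 = 40.5. One unit is then 40.5/5 = 8.1 months, and the correlation with months is 40.5/√(5 × 330.75) = 0.996. The units change, but the test hardly does. If *visit* were a four-level factor, the 1-df time interaction would become a 3-df test.

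**The case against.** Most of the other side's case is sound, and it limits the point.

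- *Scheduled coding is not proved.* The SAP never says that dates were discarded, and its fixed-effect list names a month for each visit, which could be the actual month. This stands, so the bias is conditional. Still, the values given are the scheduled ones, and that is the natural reading.
- *No delay is documented in size.* This stands. Half a month at every follow-up gives 1.7%, and the COVID rule touches only households with symptoms. Because it counts 14 days or more from the end of symptoms, longer delays are possible but not shown. Protocol Section 13.1 also withdraws participants who cannot attend or who cancel often, which limits large delays.
- *The tests are largely protected.* This stands. A reader might infer that all four hypothesis tests are biased. The documents do not support that: common lateness leaves a null interaction null, and nothing in them suggests that lateness differs by sensitization status.
- *Hypothesis 4 may simply be shorthand.* A reader might infer that it is analysed on a materially different scale. The word may only abbreviate the month term already named, and an equally spaced index would barely alter the test.
- *The label is harmless in computation.* A reader might infer that the gaps 6, 9 and 9 were entered as time. The listed values rule that out, so the label is an error of wording.

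**Conclusion.** The point holds at a modest size. Three facts are established from the text: the label contradicts the values, baseline has no stated time code, and hypothesis 4 names its time term differently from hypotheses 1 to 3. Scheduled coding is the natural reading but is not confirmed. If it was used and visits ran late on average, the slope per month is overstated by about 2% to 10% for uniform delays of 0.5 to 3 months, and by about 12% for delays of 1, 2 and 3 months. These figures assume the delays, complete data, linear growth and baseline entered at 0. They describe the scale of the estimates. A true-null sensitization-by-time test is biased only if lateness differs by sensitization status, which the documents neither show nor exclude. Actual elapsed time removes the problem whichever way visits ran.

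**What to change.** 1. In all four models, define time as continuous months from the Visit 1 date to the actual visit date, with baseline = 0.
2. Use this same variable in hypothesis 4 in place of *visit*.
3. Correct the label so that 6, 15 and 24 are described as scheduled months since Visit 1, and state that baseline rows enter at 0.
4. Keep scheduled months as a sensitivity analysis, and report the distribution of actual minus scheduled timing by sensitization status. That shows directly whether differential lateness is a concern.
5. Reconcile the planning table in protocol Section 20.3, which describes follow-up at 6-month spacing, with the 6, 15 and 24 months used elsewhere.

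The SAP is written in the past tense, so the cost is refitting four models as well as rewording. This assumes that visit dates were recorded, which is a reasonable inference for scheduled in-person appointments but is not stated. If actual dates were already used, one sentence saying so settles the scheduled-versus-actual question; items 2, 3 and 5 remain as wording corrections.
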